**Aim 3) To determine whether the LPS present in the sera from lean high fat fed, obese, and T2DM subjects mediates the insulin resistance, and whether this effect is mediated via TLR4.** In this Aim we will test the hypotheses that sera from lean high fat fed, obese, and T2DM subjects (from Aims 1 and 2) will induce an inflammatory response (activation of inflammatory signaling cascades) and impair insulin action in cultured primary myotubes obtained from lean individuals, and that the sera from these groups (lean on high fat diet, obese, and T2DM), when treated with LPS-reducing agents (synbiotic and sevelamer), will blunt the inflammatory response and insulin resistance. We will also specifically neutralize LPS in the sera from these subjects (lean on high fat diet, obese, and T2DM) using polymixin B, and will block TLR4 signaling in the myotubes with short hairpin (sh)RNA and a pharmacologic inhibitor (TAK242), to test the hypothesis that the inflammatory state and insulin resistance caused by the sera occurs via an LPS-TLR4-mediated mechanism.

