**Experiment 1. Does sera from lean high fat fed, obese, and T2DM induce inflammation and insulin resistance and are these effects ameliorated by *in vivo* treatment with the synbiotic and sevelamer?**

Human myotubes are treated with sera from (i) lean subjects studied in Aim 1 who ingested a low and high fat diet and received the synbiotic, sevelamer, and placebo; and (ii) lean, obese and T2DM subjects who received the synbiotic, sevelamer, and placebo (Aim 2). Treatments are conducted in a time-dependent (24h and 48h) and dose-dependent (10%, 20% and 40% serum in MEM culture media) manner. After these incubations, cells are collected for measurement of TLR4 signaling (TLR4-MyD88 association, IKK/NFκB, MAPK, inflammatory genes) (38, 48). To assess the effect on insulin action, after treatment with the subjects' serum, cells are stimulated with insulin for 20 min. Cells are then collected in lysis buffer for insulin signaling studies (49) or subjected to a glucose transport assay (60). Increasing concentrations of insulin (0, 1, 10 and 100 nM) will be employed to determine whether the sera affects insulin responsiveness (shifting of the curve).

**Experiment 2. Does elevated LPS in the circulation mediate the inflammatory state and insulin resistance observed in muscle from lean high fat fed, obese, and T2DM subjects?** Serum samples from these subjects will be treated with polymyxin B which sequesters LPS and specifically blocks its biological

activity (61). Polymyxin B cannot be administered to human subjects due to its nephrotoxicity. However, because of its capacity to sequester LPS, ongoing multicenter clinical trials are being conducted assessing the effect of extracorporeal hemoperfusion with polymyxin B absorption columns in patients with sepsis (62). Assays of TLR4 signaling, inflammatory gene expression, insulin signaling, and glucose transport will be conducted in the presence and absence of polymyxin B (20  $\mu\text{g/ml}$ ).

**Experiment 3. Does TLR4 mediate the pro-inflammatory state and insulin resistance observed in lean high fat fed, obese, and T2DM subjects?** Myotubes from lean subjects will be treated with sera from lean high fat fed, obese and T2DM subjects, and the same experiments described in Experiment 1 will be conducted (TLR4 signaling, inflammatory genes, insulin signaling, glucose transport). To test whether the effects from the sera are TLR4-mediated, TLR4 will be blocked/inhibited using two different approaches:

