a) **TAK242**: This agent (Takeda Pharmaceuticals) binds specifically to TLR4 and inhibits signaling by preventing its interaction with the adapter proteins TRAM and TIRAP (63).

b) **shRNA**: To knock down TLR4 we will use adenoviral-driven shRNA (Vector Biolabs, Philadelphia, PA) as described by our group (38). As negative control we will use a scrambled non-mammalian sequence (Ad-scrambled). We will perform a dose-response study to determine the minimal amount of virus that will achieve maximal knock down efficient. Based on our own experience, we anticipate that this dose will be in the  $1 \times 10^2$  to  $1 \times 10^8$  PFU/ml range. Fig. 17 shows images of typical human myotubes developed in our lab infected with adenovirus tagged with green fluorescent protein. Figs. 18a and 18b show that our method is highly effective to knock down TLR4.

[figure not shown]

Figure 17.

[figure not shown]
[figure not shown]

Fig. 18b

**Interpretation and limitations.** Based on our preliminary studies (Fig. 13), we anticipate that sera from lean high fat fed, obese, and T2DM will induce an inflammatory response and insulin resistance as evidence by elevated IKK/NF $\kappa$ B and MAPK signaling and inflammatory gene expression, decreased insulin signaling, and decreased glucose transport, as compared with myotubes treated with sera from lean subjects. If our hypothesis is correct, sera from high fat fed, obese and T2DM subjects, collected after treatment with the synbiotic and sevelamer, will induce a less severe inflammatory response and insulin resistance, and the changes in LPS level after *in vivo* treatment will predict the *in vitro* response.

One limitation of this approach is that numerous systemic factors could be responsible for the inflammatory response and insulin resistance caused by sera from high fat fed, obese and T2DM subjects. If these effects are mediated by LPS, its neutralization with polymyxin B should ameliorate them. In addition, if the effect is mediated through TLR4, the inflammatory response and insulin resistance caused by the sera will be reduced/prevented by blocking/downregulating TLR4 with TAK242 and shRNA.

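### Aim 3 puts no LPS or TLR4 blocker on low-fat or lean control sera, so a fall in the response to disease sera cannot show that LPS/TLR4 explains the excess over lean serum

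*Combined protocol and SAP*

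**What the plan says.** All the relevant text is in section A (Specific Aims) and section D (Research Design and Methods) of the combined protocol and SAP.

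- **Experiment 1, no blocker.** The sera include those from "lean subjects studied in Aim 1 who ingested a low and high fat diet and received the synbiotic, sevelamer, and placebo", and lean, obese and T2DM sera from Aim 2. Control sera are present here.
- **Experiment 2, polymyxin B.** "Serum samples from these subjects will be treated with polymyxin B which sequesters LPS". The experiment's heading identifies the subjects as lean high-fat-fed, obese and T2DM. Section A gives the same list: "We will also specifically neutralize LPS in the sera from these subjects (lean on high fat diet, obese, and T2DM) using polymixin B". The control is within serum: "Assays of TLR4 signaling, inflammatory gene expression, insulin signaling, and glucose transport will be conducted in the presence and absence of polymyxin B".
- **Experiment 3, TAK242 and TLR4 shRNA.** On procedures, the text refers back to the first experiment: "the same experiments described in Experiment 1 will be conducted (TLR4 signaling, inflammatory genes, insulin signaling, glucose transport". The sera it names are narrower than in that experiment: "Myotubes from lean subjects will be treated with sera from lean high fat fed, obese and T2DM subjects". A scrambled adenoviral sequence is the negative control for the shRNA. No vehicle control is stated for TAK242.
- **Interpretation and limitations, Aim 3.** The expected effect of the disease sera is defined relative to myotubes exposed to lean sera. For LPS the text then says: "If these effects are mediated by LPS, its neutralization with polymyxin B should ameliorate them". A parallel prediction is made for TLR4 blockade.
- **Interpretation and limitations, Aim 2.** Aim 3 is given the task of testing whether group differences and intervention effects are due to changes in circulating LPS.
- **Statistical analysis.** Group means are compared by repeated-measures ANOVA. No serum-by-blocker term is named.

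**The concern.** The question put to Aim 3 is about an excess: how much of the difference between disease serum and lean serum is due to LPS acting through TLR4. Answering it needs the blocker effect in both kinds of serum. As written, the blocker effect is observed only in disease serum.

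Some effect of blocking is plausible in any serum. The planning table gives lean LPS as 0.049 (obese 0.119, T2DM 0.130), so lean serum is not LPS-free. The background section notes that saturated fatty acids also activate TLR4. If a blocker changes the response by the same proportion in every serum, the disease sera will show amelioration while the ratio of disease to lean response stays where it was. The planned experiments cannot tell that result from true removal of the excess.

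At stake is the interpretation of the in vitro mechanistic aim. No subject's treatment or safety is affected.

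**Working it through.** **The plan's own figures.** The plan gives no power or effect size for any blocker comparison. The nearest figure is MCP-1 mRNA for lean against obese serum (1.18±0.18 and 2.3±0.6, n=12 each, stated power 0.88). With pooled SD √((0.18²+0.6²)/2) = 0.443, d = 1.12/0.443 = 2.53 and the power exceeds 0.99. The stated 0.88 does not reproduce, but this point does not depend on it. The IL-6 row (0.6±0.06 and 1.2±0.06, stated 0.99) is consistent with its inputs.

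**Which cells exist**

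| Serum | No blocker | Polymyxin B | TAK242 / shRNA |
|---|---|---|---|
| High-fat lean, obese, T2DM | Yes | Yes | Yes |
| Low-fat lean (Aim 1), lean (Aim 2) | Yes (Experiment 1) | Not stated | Not stated |

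**Step 1: what a non-specific fall looks like (inflammatory mRNA only).** Assume that a blocker lowers every serum's readout by 30%.

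- IL-6, obese serum: 1.2 × 0.7 = 0.84. Apparent share of the excess removed: (1.2 − 0.84)/(1.2 − 0.6) = 60%.
- MCP-1, obese serum: 2.3 × 0.7 = 1.61. Apparent share: 0.69/1.12 = 62%.
- The obese/lean MCP-1 ratio is 2.3/1.18 = 1.95 without blocker and 1.61/0.826 = 1.95 with it. None of the relative excess has gone.

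**Step 2: how often the fall is significant in obese serum alone.** Paired t-test, n = 12, two-sided 0.05, non-central t with 11 df. SD is 0.6 without blocker and 0.6 × (1 − fall) with it. The SD of the difference is √(s₁² + s₂² − 2ρs₁s₂), with ρ assumed.

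| Fall | Mean change | ρ | SD of change | Power |
|---|---|---|---|---|
| 30% | 0.69 | 0.3 | 0.621 | 0.938 |
| 30% | 0.69 | 0.5 | 0.533 | 0.982 |
| 30% | 0.69 | 0.7 | 0.429 | 0.999 |
| 20% | 0.46 | 0.3 | 0.646 | 0.613 |
| 20% | 0.46 | 0.5 | 0.550 | 0.751 |
| 20% | 0.46 | 0.7 | 0.433 | 0.917 |

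**Step 3: does a serum-by-blocker contrast cure this?** It depends on the scale.

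- *Equal additive shift in all sera, in SDs of the blocker-induced change.* Tested in disease sera alone, shifts of 0.5, 0.8, 1.0 and 1.5 SD are significant with probability 0.35, 0.71, 0.88 and above 0.99. The contrast of disease with control serum stays at about 0.05 (simulated 0.050 to 0.054, 20,000 runs).
- *Equal proportional fall.* On the raw scale this is itself an interaction. At 30%, MCP-1 falls by 0.69 in obese and 0.35 in lean serum, and IL-6 by 0.36 and 0.18. Simulated over 20% to 30% falls and ρ of 0.3 to 0.7, with n = 12 per group, the raw-scale contrast is significant about 0.19 to 0.69 of the time for MCP-1 and 0.99 to 1.00 for IL-6. On the log scale both are about 0.05.

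**Step 4: cost in sensitivity.** At 80% power and n = 12, the detectable effect is about 0.89 SD of the blocker-induced change within one serum group. It is about 1.20 SD for the contrast of two independent groups.

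**The case against.** Several points on the other side stand.

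- **Controls are stated.** The with/without polymyxin B comparison and the scrambled sequence guard against artefacts of the procedure and the vector. Three tools acting at different points make it unlikely that one tool's off-target effect explains everything. But all three act on the LPS–TLR4 axis. A baseline contribution of that axis, present in every serum, would appear with all three.
- **Aim 3 does have lean comparators.** A reader might infer that it has none. Experiment 1 includes low-fat and lean sera without blocker, so the gap is one cell of the design.
- **Experiment 3 refers back to Experiment 1.** This could be read as bringing control sera in. The parenthesis lists assays, however, and the same sentence names the restricted sera. Experiment 2 has no such reference.
- **No rule of proof is written.** A reader might infer that any fall under a blocker will be declared proof of mediation. The interpretation section states predictions, under an acknowledged limitation that many serum factors could be responsible.
- **Insulin-action readouts run the other way.** A reader might infer that a general lowering of the readout would falsely support mediation of insulin resistance. For insulin signalling and glucose transport, mediation predicts a rise, so a general fall would count against it. The corresponding risk there is a blocker that raises insulin action in any serum.

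**Conclusion.** The point holds as a gap in the design of Experiments 2 and 3. Following the text as written, the investigators cannot separate removal of the disease-serum excess from a blocker effect that would occur in any serum, although the excess is what Aim 3 is meant to explain. The documents do not support the stronger claim that a non-specific effect will be taken as proof of LPS/TLR4 mediation.

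The size given (probability 0.61 to above 0.99 for MCP-1) is an illustration. The 20% to 30% falls and the correlations of 0.3 to 0.7 are assumed. The SD of 0.6 is taken as variation between sera, but the preliminary serum experiment described in section C used one lean and one obese donor, so it may not be. The calculation covers inflammatory mRNA only. The plan gives no data from which to size the corresponding risk for insulin signalling or glucose transport.

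**What to change.** 1. State in Experiments 2 and 3, and in Aim 3 of section A, that placebo-arm low-fat-diet sera (Aim 1) and placebo-arm lean sera (Aim 2) go through the same polymyxin B, TAK242 and shRNA/scrambled conditions. Include whatever control is used for TAK242. The Aim 1 low-fat sera pair within subject with the high-fat sera.
2. Pre-specify the serum-by-blocker contrast as the test of mediation in the statistical analysis section. Use the log (ratio) scale for expression readouts, for the reason shown in Step 3.
3. For insulin signalling and glucose transport, require a larger improvement with the blocker in disease serum than in control serum.

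**Cost.** Extra culture wells and assays, using sera and pooled myotubes already needed for Experiment 1. No new subjects, visits or biopsies. If assay capacity is limited, the control sera can be run at one serum concentration and one time point. The loss of sensitivity in Step 4 applies to independent groups. For the paired Aim 1 sera it depends on the within-subject correlation, which the plan does not give.

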**Aim 1) To determine the effect of high fat consumption on the intestinal microbiome, metabolic endotoxemia, and insulin action, in lean normal glucose tolerant subjects.** We will test the hypothesis that a high fat diet given to lean, normal glucose tolerant subjects will modify gut microbiome composition and enhance intestinal permeability, which will increase plasma LPS concentration, induce an inflammatory response in peripheral tissues (skeletal muscle), and impair insulin signaling and sensitivity. Also we will test the hypothesis that the inflammatory response and insulin resistance caused by high fat ingestion can be ameliorated by administering (i) a synbiotic (bifidobacterium and oligofructose) which protects the intestinal epithelial barrier and decreases intestinal translocation of LPS; and (ii) sevelamer, an agent which sequesters LPS in the gastrointestinal tract limiting its translocation into the circulation.

**Aim 2) To determine whether microbiome modulation and an experimental reduction in plasma LPS concentration improve inflammation and insulin action in insulin resistant (obese and T2DM) subjects.** In this Aim we will test the hypothesis that lowering LPS concentration in the circulation will improve systemic (muscle) inflammation and glucose metabolism in insulin resistant (obese and T2DM) subjects by protecting the intestinal barrier with a synbiotic (bifidobacterium and oligofructose) or by sequestering LPS in the gastrointestinal lumen with sevelamer.

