### C) PRELIMINARY RESULTS

**Plasma LPS concentration is increased in obese and T2DM individuals.** We measured plasma LPS in 11 lean (BMI=24.6 kg/m^2, age=41 y, fasting glucose=93 mg/dl, M value=11.3 mg/kg.min), 9 obese, nondiabetic (BMI=31.5, age=47, glucose=92, M=8.1), and 10 obese, T2DM (BMI=34.2, age=48, glucose=145, M=4.2) subjects. Insulin sensitivity (M) was measured with a hyperinsulinemic (80 mU/m^2.min) clamp. As shown in Fig. 2, the plasma LPS concentration was significantly elevated in the obese and T2DM subjects. It is important to note that a normal value for LPS concentration in human plasma has not been established and there is enormous variability in the concentration reported in normal subjects, from the 0.01 (32, 33) to the 10 EU/ml (34) range, depending on the method employed, reagent manufacturer, and population studied.

**LPS causes insulin resistance in muscle *in vitro*.** We pre-treated cultured L6 (rat) myotubes with 100 ng/ml LPS for 4 and 24 h, followed by stimulation with 100 nM insulin for 20 min. LPS significantly reduced insulin-stimulated glucose (2DG) transport (Fig. 3).

**Pharmacologic inhibition of TLR4 protects against LPS-induced inflammation *in vitro*.** We examined the effect of TAK242 (Takeda Pharmaceuticals), an inhibitor of TLR4, on LPS-induced inflammation. L6 myotubes were pre-incubated with/without 1 $\mu$ M TAK242 for 1 h, prior to stimulation with 100 ng/ml LPS for 1h. TAK242 completely blocked LPS-induced JNK (Fig 4a) and p38 phosphorylation (Fig 4b).

**LPS causes insulin resistance in human muscle cells.** The data shown

above clearly indicate that LPS impairs insulin action in rodent muscle cells. Also we have tested the effect of

In addition to the mouse studies described above, the role of LPS in triggering systemic inflammation also has been evaluated in healthy human subjects. Mehta et al. found that a low dose intravenous bolus

[figure not shown]
[figure not shown]
[figure not shown]

[figure not shown]
Fig 2. LPS plasma concentration

[figure not shown]
[figure not shown]

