(ii) Sevelamer: This agent is a non-absorbable, cross-linked polymer that has strong LPS-binding capacity, and therefore limits intestinal wall translocation of LPS (41). Sevelamer also has affinity for phosphates and it is FDA-approved for use as a phosphate binder in patients with chronic kidney disease. Sevelamer does not cause hypophosphatemia in individuals with normal kidney function (42, 43). We have confirmed sevelamer's ability to reduce LPS concentration *in vitro* and to inhibit LPS-induced inflammatory response using our primary

human muscle cell culture system and isolated rat muscle preparation (Fig.12). A cross-sectional study found that subjects who take sevelamer have lower LPS concentration (35) and prospective studies have shown that sevelamer reduces LPS concentration in humans as much as 80% (36, 37). We have confirmed sevelamer's LPS-lowering effect in our study population (Fig. 11). Based upon its ability to sequester LPS in the intestinal lumen, sevelamer's systemic anti-inflammatory and immune-modulating properties are being tested in a large NIH-sponsored multi-center (20 academic sites) trial, in otherwise healthy HIV-infected subjects with normal renal function (<https://actgnetwork.org>).

[figure not shown]

Figure 14. Study design (Aim 1)

**Subjects.** 36 (completers), healthy, lean (BMI <26 kg/m^2) normal glucose tolerant subjects, aged 18-65 years, without a family history of T2DM, will be enrolled (50% males). Subjects will be randomized to receive a low or a high fat diet for 4 weeks. After a 10-12 week washout period, subjects who first received the low fat diet, will then receive the high fat diet for 4 weeks, and vice versa (each subject will be its own control). During the time the subjects receive these diets, they will simultaneously receive in a randomized double-blind fashion (i) placebo, (ii) synbiotic or (iii) sevelamer (n=12 completers per group). The protocol is outlined in Fig. 14.

**Inclusion Criteria:** 1) Both genders. All races and ethnic groups.

2) Premenopausal women in the follicular phase, non-lactating, and with a negative pregnancy test.

Postmenopausal women on stable dose of or not exposed to hormone replacement for ≥6 months.

3) HCT ≥ 34%, serum creatinine ≤ 1.4 mg/dl, electrolytes, urinalysis, and coagulation tests. LFTs up to 2X.

4) Stable body weight (±2%) for ≥ 3 months. Two or less sessions of strenuous exercise/wk for last 6 months.

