collected in the postprandial state, and this will allow us to evaluate acute postprandial changes in chylomicron LPS content and plasma LPS level, and how these relate to measures of insulin action.

**Specific Aim 2) To determine whether microbiome modulation and an experimental reduction in plasma LPS concentration improve inflammation and insulin action in insulin resistant (obese and T2DM) subjects.**

**Rationale.** Obese and T2DM subjects have alterations in the intestinal microbiome (lower content of beneficial bacteria such as Bifidobacteria) (5), abnormal gut permeability (24, 53), increased plasma LPS (preliminary data) (54, 55), and elevated TLR4 signaling in muscle (38) and monocytes (56). In this Aim we will test whether protecting the intestinal barrier with a synbiotic will restore normal gut permeability, reduce LPS, and ameliorate inflammation (TLR4 signaling) and insulin resistance. To assess the role of LPS independently, also we will reduce plasma LPS concentration with sevelamer.

**Subjects.** 36 (completers) lean ( $BMI < 26 \text{ kg/m}^2$ ) normal glucose tolerant, 36 (completers) obese ( $BMI = 30-37$ ) normal glucose tolerant, and 36 (completers) obese ( $BMI = 30-37$ ) T2DM subjects will be studied. 12 subjects per group will receive the synbiotic (oligofructose plus Bifidobacterium longum), 12 sevelamer, and 12 placebo. We will study an equal number of males and females. Other inclusion and exclusion criteria are similar as described in Aim 1, except that T2DM subjects ( $Hb_{A1c} \leq 8.5\%$ ) will be enrolled. The only antidiabetic drugs allowed are sulfonylureas, due to their minimal effect on muscle physiology and inflammation. Sulfonylureas will be held for 48 h before any procedure to avoid hypoglycemia during fasting.

**Design. Visit 1:** Subjects will undergo a medical history, physical examination, and screening blood tests.

**Visit 2:** Within 3-14 days eligible subjects will return for OGTT.

**Visit 3:** Within 3-14 days subjects undergo blood (LPS) and stool collection and an intestinal permeability test.

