**Interpretation and limitations.** We expect that the obese and T2DM subject will have an unfavorable intestinal microbiome profile (decreases in Bifidobacteria and Bacteroidetes) (54, 55) which will be associated with enhanced intestinal permeability and increased LPS level. Thus, we expect that these subjects will have an elevated inflammatory tone (TLR4 signaling) in muscle, which will reduce insulin action. Based upon previous animal studies (23-25), we anticipate that the synbiotic will restore gut epithelial integrity, decrease circulating LPS level, and ameliorate insulin resistance in obese and T2DM subjects. We also anticipate that sevelamer will decrease LPS concentration (36, 37) and will lead to reduced inflammatory signaling (IKK/NF $\kappa$ B, MAPK, inflammatory genes) in muscle. Because sevelamer's effect is to reduce LPS, also we anticipate that flux through TLR4 (TLR4-MyD88 association) will be lower. In addition, we expect that the reductions in LPS concentration will predict (correlate with) changes (reductions) in TLR4 signaling and improved insulin action.

Aim 1 will test whether a fat-rich diet alters the gut microbiome and disrupts the intestinal barrier in lean subjects resulting in increased LPS translocation. The goal of Aim 2 is different; in this Aim we are proposing a proof-of-principle experiment to evaluate whether modulating the microbiome and lowering plasma LPS improves insulin action in obese and T2DM subjects. We anticipate that modulating the microbiome and plasma LPS concentration will decrease inflammation and insulin resistance in these individuals. If these changes are the result of protection of gut barrier integrity from the increased fat intake which is common in obese and T2DM subjects, then sevelamer and the synbiotic also should prevent the inflammatory response and insulin resistance caused by the high fat diet in the lean subject from Aim 1. If the lean subjects are not protected from the high fat diet, but the obese and T2DM subjects benefit from sevelamer and the synbiotic, then improvements in inflammation and insulin action are likely caused by a mechanism different from protection against fat-induced damage. Other possible mechanisms by which LPS sequestration and/or microbiome modulation could improve inflammation and insulin action include changes in fructose-mediated endotoxemia (57), food energy extraction (9), appetite (10-13), bacterial flagellin levels (14), and peptidoglycans (15).

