TLR4 regulates numerous signaling cascades, including IKK/NF $\kappa$ B, JNK, ERK, p38 and SOCS. One or more branches downstream of TLR4 might be responsible for the negative effect of LPS on glucose metabolism. Dissecting the role of each of these branches in LPS-induced insulin resistance is beyond the scope of this grant application. Nonetheless, using our primary cell culture system and shRNA, in the future we could perform an in-depth analysis about the contribution of each of these signaling branches.

**Statistical analysis.** Experimental results will be expressed as means  $\pm$  SE. Comparisons of means between all the groups will be done by ANOVA for repeated measures (67). Associations between measures of LPS concentration vs. TLR4 signaling and vs. insulin signaling/sensitivity, within a group, will be determined by Pearson's correlation. For tests of correlation coefficients between groups we will use the Fisher's Z transformation (64). We will also determine the relationship between plasma LPS concentration vs. TLR4 signaling and LPS vs. insulin signaling/sensitivity, by using multiple regression analysis. Scatter plots will be done to look for outliers and to verify linearity. [name] is an experienced biostatistician who will direct the statistical analysis of this study. Based on our preliminary results and data from the literature (36, 65) regarding the variability of these measurements, we calculated that an  $n=12$  subjects/group is required to obtain power  $(1-\beta)$  of 0.80 with a 2-sided test at  $\alpha=0.05$  significance level. Assuming a  $\sim 20\%$  dropout rate, 15

subjects/group would be sufficient to achieve the required group sizes. The following data and power analysis (2-tailed) were obtained from an ongoing human study (PI: [name]).

Variable	Mean±SD Lean	N	Mean±SD Obese	n	Power
LPS Concentration	0.049±0.055	12	0.119±0.014	12	0.99
Insulin Sensitivity (M)	11.3±2.8	12	8.1±2.4	12	0.91
Ins Stim IRS1-P-Y	4.0±1.1	12	0.9±0.6	12	0.99
Variable	Mean±SD Lean	N	Mean±SD T2DM	n	Power
LPS Concentration	0.049±0.055	12	0.130±0.071	12	0.99
Insulin Sensitivity (M)	11.3±2.8	12	4.2±1.7	12	0.99
Ins Stim IRS-1 P-Y	4.0±1.1	12	1.5 ±1.0	12	0.99

For the following variables, data were obtained from published human studies (36, 40, 65).

Variable	Mean±SD Pre-Sevel	N	Mean±SD Post-Sevel	n	Power
LPS Concentration	3.6±3.0	12	1.2±2.3	12	0.99
CRP Concentration	4.8±2.4	12	0.44±0.24	12	0.99
Variable	Mean±SD Placebo	N	Mean±SD Synbiotic	n	Power

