LPS Concentration	87±14	12	54±10	12	0.99

We performed the following calculations (two-tailed) using data from our preliminary *in vitro* experiments:

Variable	Mean±SD Lean Serum	n	Mean±SD Obese Serum	n	Power
MCP-1 mRNA	1.18±0.18	12	2.3±0.6	12	0.88
IL-6 mRNA	0.6±0.06	12	1.2±0.06	12	0.99

**Other specific methods:** **Intestinal permeability test.** Five g lactulose and two g mannitol dissolved in water are ingested, hourly urine and plasma samples are collected for 8 hours, and lactulose and mannitol are analyzed by gas chromatography (66, 67). Lactulose and mannitol permeate only in minimal amounts across the normal intestinal wall and are not metabolized by the body. In disease state, the intestine becomes preferentially permeable to lactulose than mannitol. [name] (Co-I) has previously conducted this test (68).

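### The plan gives no basis for its 0.80 power at 12 per group as it applies to a treatment effect on clamp insulin sensitivity (M), and the 0.91 printed for the lean-obese M row should be about 0.82

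*Combined protocol and SAP*

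**What the plan says.** The Statistical analysis paragraph (section D) states that 12 "subjects/group is required to obtain power" of 0.80 with a two-sided test at 0.05, and that 15 per group allows for about 20% dropout. It names no endpoint and no comparison.

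Twelve is the size of one randomised arm. In Aim 1, "they will simultaneously receive in a randomized double-blind fashion (i) placebo, (ii) synbiotic or (iii) sevelamer (n=12 completers per group"). In Aim 2, within each of the lean, obese and T2DM populations, "12 subjects per group will receive the synbiotic (oligofructose plus Bifidobacterium longum), 12 sevelamer, and 12 placebo".

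The power tables that follow come in three sets.

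- **Population gaps.** "The following data and power analysis (2-tailed) were obtained from an ongoing human study". They compare lean with obese and lean with T2DM subjects on LPS, M and insulin-stimulated IRS-1. The two M rows are lean 11.3±2.8 against obese 8.1±2.4 (printed power 0.91), and lean against T2DM 4.2±1.7 (printed power 0.99).
- **Treatment rows from published studies.** Sevelamer before and after, on LPS and CRP; synbiotic against placebo, on LPS only.
- **In vitro rows.** "We performed the following calculations (two-tailed) using data from our preliminary" experiments; these compare lean with obese serum.

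The Aim 2 hypothesis is that "lowering LPS concentration in the circulation will improve systemic (muscle) inflammation and glucose metabolism in insulin resistant (obese and T2DM) subjects". The Aim 2 interpretation calls the study a "proof-of-principle experiment to evaluate whether modulating the microbiome and lowering plasma LPS improves insulin action in obese and T2DM subjects".

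**The concern.** An unqualified 0.80, attached to the size of a randomised arm, invites the reader to apply it to every hypothesised outcome. That includes whether the synbiotic or sevelamer changes M. The gap between lean and obese people says how far apart two populations are; it does not say how far four weeks of treatment will move M. At the Aim 2 baseline, moreover, the population contrast has 36 against 36, not 12 against 12.

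What is at stake is the reading of a null result on M. If the reader believes that power was 0.80 for a relevant effect, a null result counts as evidence against an effect. If the trial could detect only a large change, it does not. The plan states neither a target effect on M nor the smallest effect that 12 per arm can detect.

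**Working it through.** **Inputs from the documents.** M (mg/kg.min): lean 11.3, SD 2.8; obese 8.1, SD 2.4; T2DM 4.2, SD 1.7. There are 12 completers per arm and 36 per population; alpha is 0.05 two-sided and target power 0.80.

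**Assumption.** The documents give no within-subject correlation ρ for M, so 0.5/0.7/0.8/0.9 is used throughout, with equal SD at both measurements.

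**1. The plan's own figures.** Dropout: 12/(1−0.20) = 15, as stated. For the lean-obese M row:

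- pooled SD = √((2.8² + 2.4²)/2) = 2.61; d = 3.2/2.61 = 1.227
- t-test power (noncentral t, noncentrality d√(n/2), 2n−2 df): 0.78 at n=11, **0.82 at n=12**, above 0.99 at n=36
- normal approximation at n=12: 0.85

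So 12 is the smallest n that reaches 0.80 by t-test on this cross-sectional row, but the printed 0.91 is not its two-tailed power. A one-sided normal approximation gives 0.913, which may explain it. The lean-T2DM M row does reproduce (above 0.99).

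**2. Other rows, same method, 12 per group.**

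| Row | Printed | Computed |
|---|---|---|
| LPS, lean-T2DM (0.049±0.055, 0.130±0.071) | 0.99 | 0.85 (t); 0.88 (normal) |
| LPS, before/after sevelamer (3.6±3.0, 1.2±2.3) | 0.99 | 0.56 unpaired |

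For the sevelamer row analysed as paired, the SD of the difference is √(3.0² + 2.3² − 2ρ·3.0·2.3). It is 2.72 at ρ=0.5 (power about 0.80) and 1.80 at ρ=0.8 (power about 0.99).

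**3. Randomised contrast on M.** For 0.80 power the standardised difference is d = 1.197 at 12 against 12. The SD of a within-person change is SD·√(2(1−ρ)), and the minimum detectable difference is d times that. Example, obese at ρ=0.7: 2.4 × √0.6 = 1.86, and 1.197 × 1.86 = 2.22.

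| Contrast | ρ = 0.5/0.7/0.8/0.9 | % of mean M |
|---|---|---|
| Aim 2 obese, active minus placebo | 2.87/2.22/1.82/1.28 | 35/27/22/16 |
| Aim 2 T2DM, active minus placebo | 2.03/1.58/1.29/0.91 | 48/38/31/22 |
| Aim 2 lean, and Aim 1 diet × treatment | 3.35/2.60/2.12/1.50 | 30/23/19/13 |

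If obese and T2DM were pooled (24 against 24), d = 0.826 and SD = √((2.4² + 1.7²)/2) = 2.08. The differences are 1.72/1.33/1.09/0.77.

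**4. Aim 1 diet effect, each subject as own control.** This is a paired test with SD 2.8·√(2(1−ρ)), ignoring period and arm terms. The standardised difference needed is 0.480 at n=36 and 0.889 at n=12.

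| Contrast | ρ = 0.5/0.7/0.8/0.9 | % of 11.3 |
|---|---|---|
| All 36 completers, averaged over arms | 1.34/1.04/0.85/0.60 | 12/9/8/5 |
| Placebo arm only, n=12 | 2.49/1.93/1.57/1.11 | 22/17/14/10 |

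**5. Sensitivity to method.** Baseline-adjusted ANCOVA (SD·√(1−ρ²), 21 df) gives 2.49/2.06/1.73/1.25 in obese and 1.77/1.46/1.22/0.89 in T2DM. A pooled-error repeated-measures ANOVA lowers d only to 1.18 (33 df) or 1.15 (99 df).

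**The case against.** The best defence is that the basis is disclosed. The general sentence refers to the variability of the measurements, and each table then labels its variable, contrast, means and SDs. No row claims a treatment effect on M. The documents name no primary endpoint; LPS is the variable that treatment is meant to lower, and it has treatment rows for both agents. Aim 1's interpretation names Rd as the clamp measure, so choosing M as the test case is an inference from the power tables. This stands as far as it goes: the fault is an unqualified sentence above labelled tables, not a false treatment row. It does not supply support for M, since power for LPS does not carry over to a separate hypothesised outcome.

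It is also fair that Aim 1's title question is the diet effect, which is much better placed than the treatment contrast: over all 36 completers the detectable difference is 12% of lean M at ρ=0.5. Any account of M should show it. And repeated measures do add power, but by an amount that depends on a correlation the plan does not give.

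A reader might infer that the trial is underpowered for insulin sensitivity. The documents do not support that. With a large enough effect, a high within-subject correlation or a pooled analysis, 12 per arm could reach 0.80. As an illustration only, since the plan sets no target, a 20% change in obese subjects (1.62) has power 0.35 at ρ=0.5 and 0.94 at ρ=0.9.

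A reader might also see a contradiction in the clamp rates. In the Preliminary Results, "Insulin sensitivity (M) was measured with a hyperinsulinemic" clamp at 80 mU/m².min, while Aim 1 Visit 5 uses 60. These are two different studies, so this bears at most on whether the planning SDs carry over.

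**Conclusion.** The point holds in two parts of different strength.

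First, the 0.80 is unsupported for the randomised treatment effect on M in both aims, because every M row is a difference between populations. This is missing support, not a demonstrated shortfall. The detectable differences rest on the plan's cross-sectional SDs and on assumed correlations, and they vary more than twofold over the assumed range. They show what 12 per arm can detect; they cannot settle whether that is adequate.

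Second, the 0.91 for the lean-obese M row is an arithmetic error as a two-tailed test at 12 against 12; the figure is about 0.82. This part needs no assumption beyond the printed means, SDs and n. The error does not bring that row below 0.80.

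The matter should be fixed because it changes what a null result on M can be taken to show. It does not call for a change in sample size.

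**What to change.** (a) Limit the 0.80 sentence to the variables and contrasts in the tables. Correct the lean-obese M row from 0.91 to about 0.82. Recheck the other rows before relying on them, in particular LPS before and after sevelamer (stating whether it is paired and at what correlation) and LPS lean against T2DM.

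(b) Add one table of minimum detectable differences in M (80% power, two-sided 0.05), in mg/kg.min and as a percentage of mean M, with the assumed correlation shown as a range. It should cover Aim 2 active-minus-placebo change in obese, T2DM and lean subjects separately, Aim 1 diet × treatment, and the Aim 1 within-subject diet effect (36 completers, and placebo arm alone). The figures in the working can serve.

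(c) If an estimate pooled over obese and T2DM is intended, say so and give the 24 against 24 figures.

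A footnote may record that the planning M values came from an 80 mU/m².min clamp.

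The cost is a change of wording and one small table. No subjects are added and no procedure changes; the downside is a less favourable stated figure for M.
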